#### Exploratory Outcomes:

1. To compare patient satisfaction with different non-ablative and ablative energy-based therapies for rejuvenation of the scalp, face, neck/décolletage, hands, upper and lower extremities, trunk and vagina.
2. To determine the adverse event profile for different non-ablative and ablative energy-based therapies for rejuvenation of the scalp, face, neck/décolletage, hands, upper and lower extremities, trunk and vagina.

As the majority of the population ages, therapies for the improvement of skin and skin appendage disorders are becoming ever more popular for patients to ask for, and for clinicians to provide. Currently there are multiple options for skin improvement including non-invasive, minimally invasive and invasive surgery. Invasive surgeries often provide the most impressive results, however are also accompanied by a greater adverse event profile. Non-invasive therapies such as topicals (e.g. vitamin A, vitamin C, anti-oxidant serums) and chemical peels, provide nominal side effects, however results obtained using these treatments are often slight and unimpressive. Minimally invasive procedures such as fillers, botulinum toxin, radiofrequency, lasers and microneedling offer the best of both worlds with adequate results and a minimal adverse events profile with little down-time post-procedure.

The use of non-ablative (including UV lasers) and ablative devices for skin improvement is a “hot topic”. This encompasses the correction of wrinkles/rhytides, dyspigmentation, redness, skin texture (elasticity and laxity), epidermal thinning, hyper- and hypopigmentation, and skin appendage disorders. By creating minimal injury to the epidermis, these devices initiate the wound healing process, collagen remodeling and neocollagenesis, all leading to a refreshed and rejuvenated look. Advancements in technology has allowed for a boom in devices including non-ablative and ablative lasers, as well as radiofrequency. These devices have been used with efficacy for the treatment of the scalp, face, neck/décolletage, hands, trunk, and vagina in humans. In this study we would like to compare these devices in human subjects to determine which devices provide the most results with the least amount of adverse events.

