ablative lasers are often minimal and reported as discomfort/pain during the procedure, erythema and edema post-procedure. Ablative lasers carry a higher risk of side effects secondary to stripping of the epidermis. Fractional technology has minimized these adverse events, however if the procedure is done incorrectly, patients and physicians have reported crusting and blistering. Radiofrequency heats the dermal collagen to induce collagen remodeling and production. With an increased dermal structure, this non-ablative technology improves skin laxity, texture, elasticity and wrinkles. Side effects of radiofrequency have also been reported as minimal with discomfort/pain during the procedure, erythema and edema post-procedure. Currently all of the non-ablative and ablative technologies to be explored in this research protocol have been well-tolerated by patients and have reports of high patient satisfaction.

Primary, secondary and exploratory outcome variables will depend on the adherence of patients to post-procedure care instructions and proper sun protection (sunscreen, protective clothing, sun avoidance) that will be provided at the end of their first visit (Visit 1, Day 1). There are no predictors to be applied to our outcomes.

This study group will consist of patients seeking improvement of either the scalp, face, neck/décolletage, hands, upper and lower extremities, trunk and/or vagina.

List up to ten relevant references/articles to support the rationale for the research:

1. Gold, MH. The future of non-invasive rejuvenation technology: devices. *JDD*, 16(6):s104-7, 2017.
4. Peet, JJ. Evaluation of the safety and efficacy of hybrid fractional 2940 nm and 1470 nm lasers for treatment of vaginal tissue: pilot study. 2600-003-15 Rev. A, Sciton, Inc.
5. Pozner, J, Robb, C. Hybrid fractional laser: the future of laser resurfacing. 2600-003-13 Rev A, Sciton, Inc.

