To further validate the use of energy-based devices for improvement of the skin and skin appendages, we will also include retrospective chart review of patients that had previously been treated with one of the aforementioned modalities. Physician notes and photographs will be used to determine patients' progress post-treatment. Medical records will be accessed by the physician who previously treated the patient at Gottschalk Medical Plaza. The physician will record the type of device used, the parameters under which the device was used, the area that was treated and the number of treatments received by the patient. If there are photographs available, the photos will be assessed by one of the non-treating physicians for improvement post-treatment. There will be no collection of PHI during this retrospective chart review.

The DiVa will use both wavelengths 2940 nm and 1470 nm (fractional ablative Er:YAG and non-ablative laser diode) for vaginal rejuvenation. The Fraxel Dual 1927 nm and the 1550 nm (fractional non-ablative thulium and pulsed dye) will be used for treatment of pigmentation and wrinkle reduction. The Fraxel Re:Pair 10600 nm (fractional ablative CO2) will be used for resurfacing of the skin. The resurfacing handpieces will be utilized in this study. The Halo will use both wavelengths 2940 nm and 1470 nm (fractional ablative Er:YAG and non-ablative laser diode) for skin rejuvenation. The Helios III will use the 1064/532 nm (fractional non-ablative Nd:YAG) for removal of pigmented lesions and telangiectasias. The PicoWay will use the 1064/532 nm (dual wavelength pico laser) for removal of pigmented lesions. The ThermiVa will use radiofrequency to achieve electrocoagulation in the vagina and induce rejuvenation. The PALLAS will use the wavelengths 308/311 nm (UV laser system) will be used for scalp and skin appendage disorders as well as hypopigmentation of the body. The Vbeam is a pulsed dye laser, wavelength 595nm, which will be used for treatment of vascular lesions or pigmented lesions on the face or body.

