## **Study Design**

This study will be designed as a prospective clinical trial to compare various energy-based devices for the improvement of the scalp, face, neck/décolletage, trunk, hands, upper and lower extremities, and vagina. If patients meet the inclusion and exclusion criteria for multiple treatment areas, they will be allowed to receive treatment for multiple areas. The treating physician will decide which energy-based device is best-suited to address the patients' aging concerns; although patient preference will be taken into account, ultimately the treating physician is responsible for the correct assessment of the patients' needs, the use of the appropriate energy-based devices, and the final treatment. Although this may lead to some bias, patients will be treated in the most appropriate manner for their disease. Patients will be followed for 3 months post-treatment to determine if the procedure was efficacious for rejuvenation of the treatment anatomical area.

Per statistical considerations outlined below we will be comparing non-ablative and ablative devices. For each body area studied, 10 patients will be enrolled each into the non-ablative and the ablative device groups. The decision to treat and which device will be used will be made by the physician after careful consideration of a subject's rejuvenation concern(s). Multiple devices may be used due on one subject; for instance, a subject may require facial, body and/or vaginal rejuvenation, in which case one of the devices such as the Fraxel, Halo, Helios, Vbeam, or PicoWay would be used to address the face or body with the device picked based on the subject's needs or concerns, while either the ThermiVa or the DiVa would be used for vaginal rejuvenation, and PALLAS would be used for the scalp or hypopigmentation concerns.

A retrospective electronic medical record review will also be completed as part of this study to capture patients who were previously treated with any of the aforementioned modalities for rejuvenation of either the face, neck/décolletage, hands, trunk, upper and lower extremities and/or vagina.

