The study endpoint will be 3 months. Number of laser treatments needed during this time period will be based on the patient's clinical response to each treatment (as assessed by the physician). Evaluation will occur using various validated methods including photographs, MPM imaging, the Global Aesthetic Improvement Scale, the Visual Analogue Scale, the Modified Fitzpatrick Wrinkle Scale, the Wrinkle Severity Rating Scale, the Facial Laxity Improvement Scale, the Dyspigmentation Scale, the Mid-Clavicular Nipple Distance, the Fabi Bolton Chest Wrinkle Scale, the Merz Hand Grading Scale, the Vulvo-vaginal Laxity Questionnaire, Female Sexual Function Index, International Consultation on Incontinence Questionnaire – Short Form, Severity of Alopecia Tool, Psoriasis Scalp Severity Index, Patient Global Impression of Change, and Clinician Global Impression (based on which body site and laser are used).

There are no composite variables as the primary outcomes will only be determined by the physician and subject GAISSs. Other criteria for evaluation (secondary and exploratory outcomes) include photographs, the Modified Fitzpatrick Wrinkle Scale, the Wrinkle Severity Rating Scale, the Facial Laxity Improvement Scale, the dyspigmentation scale, the mid-clavicular nipple distance, the Fabi Bolton Chest Wrinkle Scale, the Merz Hand

Grading Scale, the Visual Analogue Scale for pain, the patient diary, and the investigator-authored patient satisfaction survey.

At each study visit, the investigator/physician will collect physician and subject-reported data regarding the efficacy and adverse events associated with the procedure (Visits 2-5, Days 14-90). To define patient satisfaction, an investigator-authored survey will be completed at the last visit (Visit 5, Day 90). Photographs will be collected at all visits (Visits 1-5, Days 1-90).

Since use of the PALLAS laser is typically required twice weekly, treatment of scalp and hypopigmentation disorders will follow a separate schedule of events from the other energy-based devices. Subject will receive 24 treatments over 12 weeks (Visits 1-24), with patient and clinician assessments and clinical photos taken at every other visit (Visit 2, 4, 6, 8, 10, 12, 14, 16, 18, 20, 22, 24). A blinded clinician will also assess change in skin or hair at Visit 12 and 24. Visit 25 will consist of a one-month follow up after the three-month treatment period.

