## **STATISTICAL ANALYSIS PLAN**

Statistical analysis of the data will be limited given the small sample size. Given the scales used for evaluation, data will be recorded as continuous scores. Statistical analysis will be completed using non-parametric methods (with significant defined as  $p < 0.05$ ) due to the subjective nature of the quantitative scales of improvement used and possible skew of results. Given that multiple areas will be treated and monitored for improvement over time, we may need to apply the Bonferroni Correction. If and when dependent samples are reported (i.e. longitudinal measures on individual patients), analysis will be completed with either the Mann-Whitney-Wilcoxon Test (two observations) or Friedman's test (more than two observations). When possible, trend evaluated over time will be assessed using a non-parametric test for trends over ordered groups. Bonferroni correction will be used to account for multiple comparisons. Analysis will be completed using STATA, version 13.

Power and sample size will be determined based on primary outcome- to compare the improvement between ablative and non-ablative therapy in face, décolletage, hands, trunk, upper and lower extremities, and vagina. Given the 7 regions to compare, Bonferroni correction was used to define the new significance level as  $0.05/7=0.007$ . Sample sizes of 10 in ablative and 10 in non-ablative group in each body region achieve 81% power to show a difference in means when there is a difference of 2.0 between the null hypothesis mean difference and the actual mean at the 0.007 significance level (alpha) using a two-sided Mann-Whitney-Wilcoxon Test.

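### The physician picks the device from the patient's concern, but the ablative versus non-ablative test ignores concern and no limit is set on the conclusion, so in face and body regions case mix can look like, or hide, a device-class difference

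*Combined protocol and SAP*

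**What the plan says.** **Allocation.** Study Design does not randomise: "The decision to treat and which device will be used will be made by the physician after careful consideration of a subject's rejuvenation concern(s". It repeats this for face and body devices, and concedes the consequence in one sentence: "Although this may lead to some bias, patients will be treated in the most appropriate manner for their disease".

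**Analysis.** The Statistical Analysis Plan compares 10 ablative with 10 non-ablative patients in each region, "at the 0.007 significance level (alpha) using a two-sided Mann-Whitney-Wilcoxon Test". It mentions no stratification, matching or covariate. Background & Purpose of the Research says: "There are no predictors to be applied to our outcomes".

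**Outcome.** Study Design states that "the primary outcomes will only be determined by the physician and subject GAISSs", that is, the Global Aesthetic Improvement Scale (GAIS) whatever the concern. The wrinkle, laxity and dyspigmentation scales are secondary or exploratory.

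**Limits.** The only limitation named in the SAP is the small sample. The aim in Background is comparative: to find which devices give the most results with the fewest adverse events.

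**The concern.** When the reason for treatment decides the device, the two classes may hold patients with different problems. If those problems improve by different amounts on the GAIS, the rank test compares case mix and device class together and cannot separate them. A significant regional result could then be credited to class when it reflects who was treated, or a real class difference could be cancelled. Neither the Bonferroni level nor more patients removes this. Blinded review of photographs deals with rater bias, not with who received which class.

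The plan admits the possible bias but attaches no analysis step and no restriction on interpretation. A team that followed the document exactly could report a class difference as a device effect.

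**Working it through.** **1. The plan's own figures.** The level is 0.05/7 = 0.00714, given as 0.007. The 81% power cannot be reproduced directly because no SD is stated. With 10 v 10, the exact two-sided rank-sum test at 0.007 rejects at U ≤ 15 or U ≥ 85, an attained level of 0.68%. Simulated power with normal scores and a difference of 2.0:

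| SD | Power |
|---|---|
| 1.08 | 82% |
| 1.09 | 81% |
| 1.10 | 80% |
| 1.25 | 67% |

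An SD near 1.08 to 1.09 is therefore consistent with the plan. SD 1.08 is used below, as an assumption.

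**2. Is concern linked to class?** Face and body devices as described in Research Procedures, with Ellacor from Study Design:

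| Device | Class as described | Stated purpose |
|---|---|---|
| Helios III | non-ablative | pigmented lesions, telangiectasias |
| Vbeam | pulsed dye (Background calls these lasers non-ablative) | vascular or pigmented lesions |
| PicoWay | not stated | pigmented lesions |
| Fraxel Dual | non-ablative | pigmentation, wrinkles |
| Fraxel Re:Pair | ablative | resurfacing |
| Halo | ablative and non-ablative wavelengths; class not stated | skin rejuvenation |
| Ellacor | not stated | not stated |

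Vascular concerns appear only on the non-ablative side: Helios III, "fractional non-ablative Nd:YAG) for removal of pigmented lesions and telangiectasias", and Vbeam, which "will be used for treatment of vascular lesions or pigmented lesions on the face or body". Other concerns overlap. Background introduces both classes together ("This encompasses the correction of wrinkles/rhytides, dyspigmentation, redness, skin texture (elasticity and laxity") and credits fractional ablative and non-ablative lasers alike with reducing wrinkles and age spots. So there is a link, but a partial one.

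Its strength depends on the unstated classes. If Halo counts as ablative, its broad purpose allows overlap. If neither Halo nor Ellacor does, the only ablative face or body laser is Re:Pair, which is missing from Background's list of lasers to be compared.

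**3. Shift from case mix alone.** With one concern forming a share p(N) of non-ablative and p(A) of ablative patients, and a GAIS gap g between that concern and the rest:

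shift in mean difference = (p(N) − p(A)) × g

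- One-sided mix, p(A) = 0, g = 0.5: 0.2 × 0.5 = 0.1 to 0.4 × 0.5 = 0.2
- One-sided mix, p(A) = 0, g = 1.0: 0.2 × 1.0 = 0.2 to 0.4 × 1.0 = 0.4
- Mirrored mix, 80/20 v 20/80, g = 1.0: (0.8 − 0.2) × 1.0 = 0.6

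The planned difference is 2.0.

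**4. Effect on the planned test.** Simulation of the exact test, 10 v 10, SD 1.08. Ranges cover the shares shown and fixed or random splits. In the power column the mix works against a true difference of 2.0.

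| Assumed mix | Gap | False positives, no device effect (nominal 0.7%) | Power for a true 2.0 (82% unconfounded) |
|---|---|---|---|
| 20–40% v 0% | 0.5 | 0.7–1.1% | 70–76% |
| 20–40% v 0% | 1.0 | 0.9–2.2% | 52–68% |
| 80/20 v 20/80 | 1.0 | 4–5% | 37% |

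The first two rows fit the one concern that the documents tie to a single class. The third needs a second concern concentrated in the ablative group.

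**The case against.** **The bias is disclosed and deliberate.** The plan puts appropriate treatment first and says so. That is a fair reason to keep the physician's choice, and nothing here challenges it. It does not settle how the result is analysed or worded.

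**Concern is not ignored in the records.** A reader might infer that the study collects nothing that could reveal the case mix. The documents do not support that. Research Procedures makes the treatment parameters depend on concern and skin type and says that the information will be carefully recorded, although for patient care and without making clear what is covered. There is also a Visit 1 physician assessment, pre-treatment photographs and a record of device and area. What stands is narrower: no coded concern variable is specified and none enters the analysis.

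**Concerns overlap between classes.** They do, for wrinkles and age spots. A reader might infer from the device descriptions that concern nearly determines class, and so take the largest error rates (at 90/10 v 10/90 and a gap of 1.0, about 9–10% false positives). The documents name no concern exclusive to ablative devices. Pigment is listed by name only for devices not described as ablative, and resurfacing only for Re:Pair, so strong alignment is possible, but it is not shown.

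**It does not apply everywhere.** For the vagina the point is weak: ThermiVa and DiVa share one stated purpose, though the physician still chooses between them.

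**Conclusion.** The concern holds in this form: for face and body regions, device choice follows concern, the primary comparison takes no account of it, and no limit is placed on what may be concluded. Case mix can therefore imitate or mask a class difference.

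The size cannot be determined, because the documents give neither the mix of concerns by class nor the difference in GAIS response between concerns. Under moderate one-sided imbalance the false-positive inflation is small, to at most about 2%, while the loss of power can be material, down to about half in the worst of those cases. Larger distortions need an alignment that the documents leave open but do not establish. All these figures rest on an assumed mix, gap, SD of 1.08 and normal scores. The change should be made, because the remedy is cheap, but the comparison should not be called invalid on this ground.

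**What to change.** Keep the physician's choice of device, the planned test and the 0.007 level. Add to the SAP:

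1. At Visit 1, code for each region the concern that the treating physician targets, from a short fixed list (for example wrinkles, laxity or texture, pigment, vascular or redness), before any outcome is rated. Record the patient's other concerns as secondary. The physician's target is the right variable because it drives the choice of device.
2. State the class of every device, including Halo, PicoWay and Ellacor. Tabulate concern, skin type and baseline severity by class in each region.
3. Beside the planned test, report a concern-stratified rank test (van Elteren, exact or permutation p-value) as a sensitivity analysis, with no p-value threshold, wherever a concern has patients in both classes. Describe the remaining concerns only.
4. Word device-class conclusions as non-randomised associations. Do not attribute a difference to class in a region where no concern has patients in both classes.

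For patients already treated, use concern only where the treating notes record it, and otherwise mark it unknown. It should not be reconstructed from photographs, which cannot show what the physician was targeting.

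**Cost.** One or two coded fields, minor programming and a weaker claim. The planned test and its power are unchanged. The stratified test is weak at this size. Its approximate power for 2.0 at 0.007 is:

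| Mix | Two concerns | Four concerns |
|---|---|---|
| Balanced | 73% | 57% |
| 70/30 or equivalent | 60% | 40% |
| 80/20 or equivalent | 36–40% | 21% |

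With two concerns split 9/1 v 1/9, its smallest exact p-value is 2 × (1/10) × (1/10) = 0.02. A non-significant stratified result must therefore not be read as no difference. Confounding by skin type or severity also remains, which is why the wording in item 4 matters most.

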## Research Procedures

We expect that screening patients for inclusion in this study will take two to three months total. Subjects will be screened for participation from the patient population of the UC Irvine, Department of Dermatology. Once a subject is chosen as a possible candidate, the research study team will discuss with the patient whether they would like to participate in a research study comparing non-ablative and ablative energy devices for skin improvement. It will be made clear to patients that modalities such as Fraxel, Halo, Helios, Vbeam, and Pico have been found to be efficacious for improvement of the skin of the face or body while ThermiVa and DiVa have been found to be efficacious for rejuvenation of the vagina, and PALLAS for the scalp or hypopigmentation disorders. Patients will be told that photographs of their scalp, face, neck/décolletage, trunk, hands, upper and lower extremities, and /or vagina depending on the treatment site will be taken and will possibly be used for publications and presentations in the future; it will be made clear to patients that all efforts will be taken to de-identify the photographs. Risks will be explained thoroughly to patients. If patients decide that they would like to participate, they will be given a copy of the informed consent either to take home and read for up to 2 weeks, or if they feel comfortable reading in a private room to read for a maximum of 2 hours before obtaining a signature. Once patients consent to participation, they will be scheduled for their first visit, which may be as early as on the same day as their screening visit.

If eligible, patients may opt to have multiple sites treated during the study.

At their first visit (Visit 1, Day 1), patients' inclusion/exclusion criteria will be reviewed, demographic information will be obtained, physician-assessment performed, vitals assessed, and photographs (before and after treatment) will be taken. Patients will then receive the energy-based treatment in one or more areas. Information regarding the area treated, the device used and the machine settings will be recorded in detail. Patients will be given a diary to fill out to assess for side effects and the timeline of resolution.

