The patients receiving laser treatments other than with the UV laser (PALLAS) will be instructed to return to the office in 2 weeks (Visit 2, Day 14 +/- 3 business days) for their next appointment where subject and physician assessments will occur and photographs will be taken. The patients will be instructed to return to the office in 2 weeks for their next appointment where subject and physician assessments will occur and photographs will be taken (Visit 3, Day 30 +/- 3 business days). The patients will be instructed to return to the office in 1 month for their next appointment where subject and physician assessments will occur and photographs will be taken (Visit 4, Day 60 +/- 3 business days). The patients will be instructed to return to the office in 1 month for their next appointment where subject and physician assessments will occur and photographs will be taken (Visit 5, Day 90 +/- 3 business days). This will be the last visit for the patients. Please refer to the attached study schedule Table 1 above for further clarification.

Subjects receiving the UV laser treatment for scalp/skin appendage disorders or hypopigmentation disorders will follow up biweekly for a total of 24 treatments (see attached study schedule table 2). Photography, clinical/patient assessments, and adverse events will be collected at each even visit. A final follow up visit will occur one month after the treatment period has completed for final clinician/patient assessments.

As optional research activities, patients will be asked if they are willing to undergo imaging using the MPM. If patients agree, they will be able to obtain baseline imaging prior to their Day 1 visit. Post-treatment imaging will be completed after 2 weeks (Visit 2), 1 month (Visit 3) and 3 months (Visit 5).

Once all subjects have completed the all visits, non-identifiable data will be complied on the industry-standard RedCAP on a secure network computer located at Hewitt Hall. Data analysis will be carried out by the personnel at the UC Irvine Dermatology Clinical Research Center. The photographs that were collected will be assessed by a blinded physician. Once data is analyzed, we hope to be able to write and publish articles summarizing our findings. Once analysis and publication is completed, non-identifying photographs and patient information will be destroyed. PHI will be maintained for 6 years after study completion.

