The number of passes, size of treated area, spot size and energy level will be determined by the treating physician/investigator. Parameters will be adjusted depending on the area being treated, the aging concern being addressed, skin type, and patients' tolerance during treatment again based on the treating physician's/investigator's discretion. The treating physicians have the appropriate knowledge and experience to be able to make these decisions during the study visit. This information will be recorded meticulously to ensure that the patient receives the proper treatment and will provide the physician/investigator with the necessary information for proper patient care and follow-up.

Subject will receive 24 treatments over 12 weeks (Visits 1-24), with patient and clinician assessments and clinical photos taken at every other visit (Visit 2, 4, 6, 8, 10, 12, 14, 16, 18, 20, 22, 24). Photographs of the subjects' scalp, faces, neck/décolletage, trunk, hands, upper and lower extremities, and/or vagina will be taken during this study. Photographs will be taken using secured cameras available for clinical photography at the Gottschalk Medical Plaza and Hewitt Hall. These photos will be uploaded immediately onto a secure server for access only by the study team.

The subject will participate in the study treatment period for 3 months. Including screening and follow up period, we expect a maximal participation period of 6 months.

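### The plan does not say who scores the physician GAIS, one of its two primary measures, or whether that rater is masked to device, and its planned blinded assessments are not tied to the primary comparison

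*Combined protocol and SAP*

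**What the plan says.** **Primary measures.** Study Design: "There are no composite variables as the primary outcomes will only be determined by the physician and subject GAISSs". I read GAISSs as the Global Aesthetic Improvement Scale (GAIS) named just before it.

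**Who rates.** At the last standard visit, "subject and physician assessments will occur and photographs will be taken (Visit 5, Day 90 +/- 3 business days"; the earlier follow-up visits are worded alike. Study Design adds that at study visits "the investigator/physician will collect physician and subject-reported data regarding the efficacy and adverse events". Neither sentence identifies the scorer or mentions masking.

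**Who chooses the device.** Study Design: "The treating physician will decide which energy-based device is best-suited to address the" patient's concerns. Research Procedures joins the two roles when it says that "spot size and energy level will be determined by the treating physician/investigator".

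**Blinded assessment.** Research Procedures: "The photographs that were collected will be assessed by a blinded physician". Study Design adds a blinded clinician, who judges change in skin or hair at PALLAS Visits 12 and 24. A non-treating photograph rater is also named, but only for the retrospective chart review.

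**Status of photographs.** Study Design: "Other criteria for evaluation (secondary and exploratory outcomes) include photographs". The Statistical Analysis Plan mentions neither a rater nor a blinded read.

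**The concern.** The Statistical Analysis Plan chooses non-parametric methods partly because it regards its scales as subjective. In a subjective global rating, knowledge of the device can colour the score. An expectation that lifts both groups equally cancels in the ablative versus non-ablative contrast. One that differs between the groups is added to the contrast or subtracted from it, and the analysis cannot separate it from a device effect.

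The plan already provides blinded readers and photographs. As written, that protection is not attached to the measure on which the primary comparison and the sample size rest.

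**Working it through.** **Step 1. The passages side by side.**

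| Question | What the text gives |
|---|---|
| Who scores the physician GAIS? | A physician, or the investigator/physician who collects the data; not identified further |
| Is that rater masked to device? | Not stated |
| Can the rater be the physician who chose the device? | Not excluded; the treating physician chooses, and treating physician and investigator are written as one role |
| What does the blinded photograph reader assess? | All collected photographs; no scale, no comparison for analysis, and no statement of what is concealed |
| What does the blinded PALLAS clinician assess? | Change in skin or hair at Visits 12 and 24; not called GAIS or primary |

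The two schedule tables cited in Research Procedures are not in the text supplied, so they could answer some of this.

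**Step 2. The plan's own figure.** Inputs from the Statistical Analysis Plan: 10 v 10 per region, difference 2.0, two-sided Mann-Whitney-Wilcoxon test, alpha 0.05/7 = 0.00714 (stated as 0.007), power 81%. No SD is given, so 81% can be neither reproduced nor refuted. Solving for the SD that yields 81% gives 1.09 to 1.25, depending on the approximation. The exact test with normal data has about 80% power at SD 1.1. I therefore use SD 1.1, with 1.25 and 1.5 as wider assumed values.

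**Step 3. Illustration of a differential leaning.** Let U be the number of the 10 × 10 = 100 cross-group pairs in which the ablative score is the higher. Reject if U ≤ 15 or U ≥ 85. The exact level is 2 × P(U ≤ 15) = 0.00684; a cut-off of 16 would give 0.00893, above 0.007. If the true difference is δ and the leaning is b, the observed difference is δ + b. The value b = 0.5 is assumed; it is 0.5/2.0 = one quarter of the planned difference. Data are simulated as normal, for one region and one rating, with 1,000,000 runs per false-positive setting.

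| SD (assumed) | False positives, b = 0 | b = 0.25 | b = 0.5 | Power, δ = 2.0, b = 0 | Power, δ = 2.0, b = −0.5 |
|---|---|---|---|---|---|
| 1.1 | 0.67% | 1.30% | 3.57% | 80.1% | 49.0% |
| 1.25 | 0.67% | 1.14% | 2.81% | 66.6% | 36.7% |
| 1.5 | 0.68% | 1.00% | 2.08% | 46.6% | 23.1% |

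With b = +0.5 the observed difference is 2.5, and at SD 1.1 the test rejects about 96% of the time.

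**Step 4. Sensitivity to coarse scores.** With scores rounded to an assumed five-point scale and a tie-corrected normal approximation, false positives are about 0.5% with no leaning. With a 0.5-point leaning they are 2.70%, 2.15% and 1.58% at SD 1.1, 1.25 and 1.5.

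I give no rate across the seven regions, because patients may contribute several regions and the regions are then not independent.

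**The case against.** **Blinding is already planned.** This stands as a correction to anyone who infers that no blinded assessment exists. It does not answer the point, because neither blinded assessment is given the GAIS or a place in the primary comparison. Nor should one say that the photograph read lacks any time point. All collected photographs are to be read, and the standard schedule includes Day 1 and Day 90. What is missing is which comparison counts.

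**The treating physician is not named as the rater.** Correct. A reader might infer that the primary physician rating is made, unmasked, by the physician who chose the device. The text permits that reading but does not state it, and the missing schedule tables might settle it.

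**Masking repairs little.** Largely true. Device choice by the physician confounds the contrast whoever rates it, and the protocol concedes that this choice may introduce bias. The subject GAIS stays open-label. Masked rating removes one source of bias from one of two primary measures.

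**The figures are not evidence of harm.** Also true. Leaning and SD are assumed, and any shift of 0.5 point from any cause would give the same numbers.

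**Stating the rater would be enough, and photographs lose information.** Stating the rater cures the unclear wording but leaves a possibly unmasked primary rating. The loss is real, since photographs show texture and laxity less well. Using the blinded score as a prespecified sensitivity analysis would be defensible. I prefer it in the primary comparison because the reader is already planned and the live score can be reported beside it.

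**Conclusion.** The concern holds as a gap in the definition of a primary measure. In the text supplied, the physician GAIS has no identified rater and no stated masking, and the planned blinded assessments are not connected to it. The change should be made, and it is inexpensive.

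The size of any bias is unknown, and so is its direction. The illustration rests on normal data, an assumed leaning of 0.5 point and assumed SDs of 1.1 to 1.5. Under those assumptions false positives per region go from 0.7% to between 2.1% and 3.6%, and power at SD 1.1 goes from 80% to 49% or 96% according to direction. A reader might take this as showing that the trial's error rate is inflated. It shows only that a 10 v 10 comparison is sensitive to a shift of that size; the documents do not show that such a shift is present. Nor would masking make the device comparison unbiased.

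**What to change.** 1. State who scores the physician GAIS and whether that person is masked to device.
2. For the regions in the Statistical Analysis Plan that can be rated from photographs, have the planned blinded physician score the GAIS from paired pre-treatment and Day 90 photographs, masked to device. Use that score as the physician GAIS in the primary comparison.
3. Report the live physician GAIS alongside it as a secondary outcome.
4. Keep the subject GAIS as the other primary measure, analysed separately and labelled open-label. Label the vaginal ratings unblinded.
5. For PALLAS, where the GAIS and a region in the primary comparison apply (scalp is not one of them), use the blinded assessment and photographs already scheduled at Visit 24. Confirm that a pre-treatment photograph is taken: the general Visit 1 text says that "photographs (before and after treatment) will be taken", but the PALLAS text lists photographs at even visits only.
6. For micro-coring, clarify which visits are meant by assessment at alternate visits. Over days 0, 30, 60, 90 and 150 it could mean 0, 60 and 150, or 30 and 90.
7. State that masked rating does not remove confounding from physician-chosen devices.

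**Cost.** Protocol and SAP wording and a scoring form. The reader is already planned, and so are the pre-treatment and Day 90 photographs for the standard devices. The downside is the weaker view of texture and laxity in photographs, which is why the live score is kept.
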